#### N.B.

- Data collectors and Health Care Worker (HCW) involving in the research will be provided with standard and adequate number of all protective gears for their personal protection. Even though, if anyone become infected all the necessary treatment will be provided from the respective hospital without any expenditure.
- Viral concentration will be estimated semiquantitatively by analyzing the 'Cycle threshold value (CT value)' following RT- PCR. The CT value is a semiquantitative value that broadly categorises the concentration of viral genetic materials (NA) is in the samples. The CT value is inversely proportional to the concentration of viral genetic materials.i.e. low CT means high concentration of viral genetic materials and high CT value is the low concentration of viral genetic materials.
- BRiCM ensures Raw material & impurities characterization and determination of shelf life by performing the stability studies as follows:

#### Raw material & impurities characterization

- PVP-I collection from approved vendor with certificate of analysis (CoA)
- Characterization tests of PVP-I such as appearance, identification, solubility, nitrogen content, iodide value, loss on drying, pH, sulphated ash and available iodine as per BP 2019 are performed in well-equipped lab of BRiCM to review the test results with the acceptance criteria stated in the specification.
- Impurity testing of PVP-I as 1-Vinyl-2-pyrrolidinone, 2-Pyrrolidinone according to British Pharmacopeia (BP) 2019 and heavy metal (Pb) as per Association of Analytical Communities (AOAC) is carried out using HPLC, LC-MS-MS, AAS & ICPMS.
- Sterile water, the diluent of 0.6% PVP-I solution is characterized by performing the tests of pH, conductivity, total organic carbon, heavy metal (Pb, As) as per American Water Works Association (AWWA), endotoxin as per European Union (EU) 85 and microbial count as per AOAC in the well-equipped Microbiology Lab of BRiCM.
- Production of 0.6% PVP-I Oro-nasal spray solution from batch dispensing to final product packing is carried out following the norms of cGMP
- In-process quality assurance/control of the product is done at real time by performing, volume check, pH of the solution, available iodine, UV absorbance as per BP 2019 and packing integrity with necessary primary and secondary packing materials.

#### Stability Study & Shelf-life estimation

- Stability studies of the product are carried out at both accelerated condition as well as real time condition as per International Council for Harmonization (ICH) guidelines applicable for Stability Zone Iva.
- Stability studies at accelerated condition is carried out at 40 deg. C up to 12 months in 2 months interval and stability studies at real time condition is carried out at 25 deg. C up to two years in three months interval.
- Stability indicting parameters such as color of the solution, pH, available iodine, UV absorbance are included in both stability studies.
- Findings of both accelerated and real time stability studies are used to predict the shelf-life of the product up to two years.

#### Period of study

The study will be carried out during the period of May 2020 to June 2021.

#### Place of study

Dhaka Medical College Hospital, Kurmitola General Hospital and Kuwait Moytree Hospital including product development & quality assurance will be held at Bangladesh Reference Institute for Chemical Measurements (BRiCM)

#### **Study Population**

18 years and above aged COVID -19 positive admitted patients of COVID-19 dedicated unit of Dhaka Medical College Hospital , Kurmitola General Hospital and Kuawit Moytree Hospital will be included in this study, who are willing to participate. Written informed consent will be taken before participation in the study. A group of healthy person (10) will be randomly selected who are interested to receive intervention (PONS) 3-4 times interval but not more than 4 time a day for 30 days.

## Selection Criteria Selection of Participants : For Group A and Group B

#### **Inclusion** Criteria

- 1. Hospital admitted patients tested positive COVID-19 within 24 hours in the laboratory by RT-PCR.
- 2. Patients with asymptomatic, mild to moderate illness of COVID-19.
- 3. Age group 18 year and above.
- 4. Consent of the patients, wish to be included in the study willingly.

#### N.B.

• Patient with moderate symptoms are normally get admitted in Hospital, who will be included in Group-A.

The intervention Group-A will receive Oronasal spray containing PVP-I and control group will receive distilled water containing oronasal spray.

As all participants of Group-A (asymptomatic, mild, moderate) are included in the study, so they will receive the same treatment (PONS)

- Asymptomatic and mild patients having co-morbid conditions are also admitted in Hospital who will be included in Group-B.
- For Group-C Participants, pre-intervention investigation will be done (FT3, FT4 TSH etc).

#### **Exclusion Criteria**

- 1. Patients with critical COVID-19 and moderate COVID-19 with other complication.
- 2. Patients having thyroid dysfunction, pregnant or lactating mother.
- 3. It should not be used prior to or after radioiodine scintigraphy or radioiodine treatment of thyroid carcinoma.
- 4. Patients allergic to iodine should be avoided
- 5. Have participated in other clinical study
- 6. Subjects with other severe acute or chronic conditions that may increase the risk of participation in the study and study treatment, or may interfere with interpretation of study results, and judged by the investigator as not suitable for participation in this clinical trial.

#### Selection of participants of Group- C

#### **Inclusion** Criteria

- 1. Healthy individual (non COVID-19)
- 2. Age -18 years and above (as below18 years lesser concentration of drug may be required).
- 3. Consent of the participants who wish to participate.

#### **Exclusion Criteria**

- 1. Participants who has any major comorbidity.
- 2. Participants having thyroid dysfunction, pregnant or lactating mother.

3. It should not be used prior to or after radioiodine scintigraphy or radioiodine treatment of thyroid carcinoma.

- 4. Participants allergic to iodine should be avoided
- 5. Have participated in other clinical study

6. Subjects with other severe acute or chronic conditions that may increase the risk of participation in the study and study treatment, or may interfere with interpretation of study results, and judged by the investigator as not suitable for participation in this clinical trial.

## **Sampling Technique**

Random sampling procedure will be followed by using table of random numbers Admitted patients of dedicated Covid-19 hospital like KGH, KMH and DMCH will be taken after fulfilling of inclusion and exclusion criterias. Then from interested participants written informed consent will be taken. After ward randomization will be carried out to select intervention group and control group.

## Sample Size

• The minimum sample size is given by:

for a finite population  $n = (Z^2 x p x q) / d^2$ 

Where, n= sample size Z = Standard normal deviate usually set at 1.96 at 95% confidence If prevalence is not known, the value of prevalence will be considered as 50%.

So, p will be 0.5.

So, q = (1-p) = 0.50, and

d = Desired accuracy or degree of allowable error. It is usually set as 5%(0.05).

So,  $n = \{(1.96)^2 \ge 0.5 \ge 0.5\} / (0.05)^2$ 

Or, n = 384

N.B. Calculated sample size is equally applicable for both experimental (Intervention) and control group.

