## **Summary**

Povidone Iodine (Iodine with water soluble polymer Polyvinylpyrolidone) or PVP-I is a proven and time trusted antiseptic agent having best possible (99.99%) virucidal effect in it's only 0.23% concentration, against all viruses including SARS-Co, MERS-CoV; even in SARS-COV-2 due to it's nonspecific mode of action for virus killing and having no resistance [1,2]. Corona virus is transmitted by/via respiratory droplets or aerosol, produced from sneezing or coughing of infected persons to healthy individual through mouth and nose mainly [5, 6]. The routes of entry of coronavirus in human body are mouth, nose and eye. PVP-I products for gargling the throat and spraying or washing the nose may have a preventive effect on COVID-19 and if it is proved in this study following human trial, this will be a landmark research in COVID-19 pandemic.

In line of this, PVP-I containing oro-nasal spray, proposed Bangasafe, which should be regarded as PONS (Povidone Iodine oro-nasal spray) in this protocol, has been developed and proposed to use against corona virus disease. The proposed clinical trial would assess the safety and efficacy of this virucidal PONS. This oro-nasal spray is prepared following GMP guideline, easily applied and has been found to be safe and effective. The clinical trial proposed here would be conducted in Bangladesh to specifically assess the safety and efficacy concern of this oro-nasal spray among Bangladeshi citizen. For preliminary assessment of efficacy and safety, a small scale randomized controlled trial with about 200 patients who are COVID-19 positive within last 24 hours had already been taken place in Dhaka medical college hospital and the data has been collected from May 2020 to September 2020 which were very much satisfactory [Attachment 2].

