## **Objectives of the study**

#### a. Primary Objective

To assess the virucidal efficacy of 0.6% PVP-I against SARS-CoV-2 in nasopharynx and oropharynx in order to use:

- To prevent viral infection before exposure while visiting and treating COVID-19 patients, attending public gatherings, using public transport etc.
- To prevent viral infection after exposure to COVID-19 patients
- To reduce viral load in nasopharynx and oropharynx of COVID-19 patients which is supposed to reduce viral transmission through respiratory route

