#### b. Secondary Objectives

- To assess the viral load in the nasopharynx and oropharynx before and after application of 0.6% PVP-I of participants of this study.
- To assess the duration of effectivity of 0.6% PVP-I on mucosal surface of participating COVID-19 patients by testing consecutive sample hourly upto 4hr.
- To estimate the shelf-life and stability of 0.6 % PONS.
- To characterize raw materials and impurities for product development and quality control/ assurance
- To measure the safety level of  $0.6\% \underline{PONS}$  by biochemical analysis of participants blood & urine

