## Methodology

#### Study design

It will be a Multicentre, Single blind, Randomized Controlled Trial.

The participant will be divided into three groups namely Group A (384 intervention group and 384 control group), Group B (20 patient) and Group C (10 healthy person).

**Group A** Number of participants 768 COVID-19 positive, moderately ill admitted patient who will receive intervention once (2 puff 0.6% PVP-I in each nostril and 2 puff inside mouth).

Step 1: Enrollment of the study populations by applying inclusion and exclusion criteria

Step 2: Randomization to allocate experimental and controlled group by using table of random number

Step 3: Application of 0.6% PVP-I spray to experimental group and distilled water to control group

Step 4: Follow up (waiting for 2-5 minutes)

Step 5: Collection of nasopharyngeal and oropharyngeal sawab for RT-PCR test for both group

Step 6: Observation of the patients for 30 minutes for possible early adverse effects (if any) and subsequent management (if needed).

Step 7: Analysis data collection, data processing and analysis by using SPSS software.

**Group B** Number of participants 20 asymptomatic to mild COVID -19 patients to whom after single time application of PVP-I oro-nasal spray, RT-PCR test will be done hourly for 4 hours in a single day (to assess the duration of effectiveness of PVP-I oronasal spray).

Step 1: Selection of 20 patients randomly with no or mild symptoms and obtain their consent for the further tests.

Step 2: Collection of 2nd, 3rd and 4th sample from nasopharynx and oropharynx hourly

Step 3: Data collection, data processing and analysis by using SPSS software

**Group C** Number of participants 10 healthy individual who accept intervention 0.6% PVP-I oronasal spray 3-4 hours interval but not more than 4 times a day for 30 days.

Step 1: Selection of 10 healthy volunteers randomly who will be selected for using 0.6% PVP-I Oro-Nasal spray 2 puff inside both nostrils and mouth 3 to 4 times a day for one month.

Step 2: Collection of blood & urine of participants on day 0, 10, 20, 30 for determination of any change in biochemical marker (thyroid, kidney and liver functions will be done)

Step 3: Data collection, data processing and analysis by using SPSS software

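### The randomised comparison is sized with a one-proportion precision formula: no target difference or power is stated, and the 5-point accuracy describes each arm, not the difference

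*Protocol*

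**What the plan says.** The Protocol's Sample Size section uses n = Z²pq/d² with Z = 1.96. The proportion p is a default: "If prevalence is not known, the value of prevalence will be considered as 50" percent. The precision is set by convention: "d = Desired accuracy or degree of allowable error. It is usually set as 5%(0.05"). The result, 384, is carried to both arms by the note "N.B. Calculated sample size is equally applicable for both experimental (Intervention) and control group". SAP section 1 repeats the same calculation and note.

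Study design describes a randomised controlled trial with "Group A (384 intervention group and 384 control group"), comparing the spray with distilled water.

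On the outcome, Endpoints names virucidal efficacy without a scale. The N.B. after Study design supplies the only measurement scale: "Viral concentration will be estimated semiquantitatively by analyzing the" CT value from RT-PCR. The primary objective includes "To reduce viral load in nasopharynx and oropharynx of COVID-19 patients which is supposed to reduce viral transmission through respiratory route", and a secondary objective is "To assess the viral load in the nasopharynx and oropharynx before and after application of 0.6% PVP-I of participants of this study".

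The analysis is a general list of tests, including chi-square and t tests (Protocol, Data Analysis; SAP section 2). SAP section 2 adds a 95% confidence level for intervals. Neither document gives a power, a type II error, an expected rate or mean in either arm, an SD, or a difference to be detected.

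**The concern.** The formula answers the question of how many people are needed to estimate one proportion to within d. The trial asks a different question: how the outcome differs between two randomised arms. The quantity whose precision or power matters is the between-arm difference, and the plan gives no figure for it.

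This is the only size justification in either document. Without a planned difference, a reader cannot tell what effect the trial was meant to detect. The 95% interval would still allow a null result to be read, but there would be no prespecified difference to read it against. The Summary reports that "a small scale randomized controlled trial with about 200 patients who are COVID-19 positive within last 24 hours had already been taken place", yet the calculation uses the default 50% and takes no rate or SD from that trial.

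**Working it through.** **Inputs from the documents.** Z = 1.96, p = q = 0.5, d = 0.05 (Protocol, Sample Size; SAP section 1); n = 384 in each arm (Protocol, Study design).

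**Assumptions, because the documents give none.** Two-sided 5% test; power of 80% or 90%; control rates of 5%, 10%, 20% and 50%; all 384 patients per arm evaluable.

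**1. The plan's own figure.** n = 1.96² × 0.5 × 0.5 / 0.05² = 384.16. The stated 384 reproduces.

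**2. Precision in one arm.** 1.96 × √(0.25/384) = 0.0500, or 5.0 points. The stated accuracy is correct for each arm taken alone.

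**3. Precision of the difference.** 1.96 × √(2 × 0.25/384) = 0.0707, or 7.1 points. The ratio to step 2 is √2, and that ratio holds at any rate common to both arms. The value of 7.1 is a maximum, because p = 0.5 is the worst case. At an assumed 10% in both arms, the half-widths are 1.96 × √(0.09/384) = 3.0 points for one arm and 1.96 × √(2 × 0.09/384) = 4.2 points for the difference.

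**4. If the outcome is the CT value, compared as a mean.** p and d have no counterpart. For an unadjusted two-sample t test, the detectable difference in SD units is closely (z for 5% two-sided + z for power) × √(2/n):
- 80% power: (1.960 + 0.842) × √(2/384) = 0.202 SD
- 90% power: (1.960 + 1.282) × √(2/384) = 0.234 SD
- 95% half-width: 1.96 × √(2/384) = 0.141 SD

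**5. If the outcome is the proportion RT-PCR negative** (not named as an outcome in the documents). For the pooled two-proportion z test, power = Φ{[δ − 1.96√(2p̄q̄/n)] / √[(p₁q₁ + p₂q₂)/n]}, solved for δ at 80% power and n = 384:

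| Assumed control rate | Detectable increase (points) | Detectable decrease (points) |
|---|---|---|
| 5% | 5.4 | about 3.6 |
| 10% | 6.9 | 5.3 |
| 20% | 8.7 | 7.5 |
| 50% | 10.0 | 10.0 |

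Check of the last row for an increase: p₁ = 0.5, p₂ = 0.6004, p̄ = 0.5502. The numerator is 0.1004 − 1.96 × 0.0359 = 0.0300 and the denominator is 0.0357. The ratio is 0.84, which gives power 0.80.

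**The case against.** The strongest defence is that the plan does not contradict itself. Read literally, the note says that 384 applies to each group, and per arm the 5-point accuracy is true. A reader might infer that the plan promises 5 points for the difference and therefore needs 1.96² × 2 × 0.25/0.05² = 768.3, about 769, per arm. The documents make no such promise; 7.1 points is the corresponding figure for the comparison, not a broken commitment.

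A reader might also take d = 5% as the difference to be detected and conclude that the trial is underpowered, since power for 50% v 55% is about 28%. The documents do not support that either: d is a precision, and no target difference is stated. By coincidence, 384 is close to the 388 per arm needed for 50% v 60% at 80% power, but that target is not stated either.

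Three further points are fair.
- Patients enter RT-PCR positive, are tested again after the spray, and chi-square is among the listed tests. A positive/negative outcome is therefore plausible, and p and d lose their meaning only on the CT reading.
- One secondary objective speaks of viral load before and after application. A baseline-adjusted analysis would change the detectable CT difference.
- No size statement can be completed until the primary outcome has a scale.

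These limit the claim without removing it. Sizing by precision is legitimate when the precision is that of the quantity being estimated. Here it is not, and no power or target difference stands in its place.

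**Conclusion.** The concern holds as a defect in the justification, not in the number. The only basis given for randomising 768 patients is a formula for a single proportion. Its accuracy does not describe the between-arm comparison, and no difference, power, control rate or SD is stated.

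The 5.0 v 7.1 point contrast follows from the plan's own inputs. The detectable differences rest on the assumed two-sided 5% test, the assumed power and control rates, full evaluability and an unadjusted analysis. Whether 384 per arm is enough cannot be judged from the documents, because they do not say what it should be enough for. This should be fixed, but it does not establish that the trial is too small.

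**What to change.** The note is wrong as written for a two-arm comparison. Keep 384 per arm and restate the figure. In the Protocol's Sample Size section and SAP section 1, name the primary outcome scale and replace the note with:

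> d = 0.05 describes each single arm only; for the between-arm comparison with 384 evaluable patients per arm, two-sided 5%:

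followed by the line that matches the outcome.

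- If CT value: *unadjusted two-sample t test, 80% power for a mean difference of about 0.20 SD and 90% for about 0.23 SD; 95% half-width 0.14 SD.*
- If proportion RT-PCR negative: *pooled two-proportion z (chi-square) test, 95% half-width for the difference at most 7.1 points; 80% power for an increase of about 5.4, 6.9, 8.7 or 10.0 points from assumed control rates of 5%, 10%, 20% or 50%.*

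Beside it, state the difference considered worth detecting, with the reason, and the power that 384 per arm gives for it. Without that sentence the insert would only describe the existing size and not justify it. If the preliminary trial measured the same outcome, its control rate or SD can replace the assumed values.

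The cost is rewording in two sections, once the outcome scale has been chosen. The downside is a less favourable stated precision: 7.1 points instead of 5 at p = 0.5.

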## **Sampling Unit**

Individual study subject i.e. selected each participants will be considered as a sample unit.

## **Data Collection instrument and Technique**

A preformed semi structured questionnaire and a check list will be used as data collection instrument. Besides medical history sheet and investigation papers of respective participants will also be used. Face to face interview will also be taken.

After receiving written permission from respective hospital authority and obtaining written informed correct data collection will be started. Study personnel at the site will enter data from source documents corresponding to a subject's visit into the protocol-specific paper CRF(Case report form). Subjects will not be identified by name in the study database or on any study documents to be collected by the principle investigator but will be identified by a site number, subject number and initials.

For paper CRFs: If a correction is made on a CRF, the study staff member will line through the incorrect data, write in the correct data and initial and date the change.

The Investigator is responsible for all information collected on subjects enrolled in this study. All data collected during the course of this study must be reviewed and verified for completeness and accuracy by the Investigator. A copy of the CRF will remain at the Investigator's site at the completion of the study (Annexure 3).

## **Data Processing**

Everyday in later part of the evening collected data will be scrutinized thoroughly to check its consistency and cohesiveness of nearing quality to entre in draft data which will be saved in computer for future use. At the same time necessary coding, editing and cleaning of data will be done. Collected data will be preserved in master data sheet as per objectives and key variables.

All procedures for the handling and analysis of data will be conducted using good computing practices meeting FDA guidelines for the handling and analysis of data for clinical trials. In this regard latest SPSS software version will be used for statistical analysis.

## **Data Quality Control and Reporting**

After data have been entered into the study database, a system of computerized data validation checks will be implemented and applied to the database on a regular basis. All changes to the study database will be documented.

#### Archival of Data

The database is safeguarded against unauthorized access by established security procedures; appropriate backup copies of the database and related software files shall be maintained. Databases are backed up by the database administrator in conjunction with any updates or changes to the database.

At critical junctures of the protocol (e.g. production of interim reports and final reports), data for analysis is locked and cleaned per established procedures.

#### Availability and Retention of Investigational Records

The Investigator must make study data accessible to the monitor and authorized representatives of the principle investigator. The Investigator must provide interim study report with data at every three months interval to the principle investigator. As per requirement study report and data may be provided to BMRC and DGDA. A file for each subject must be maintained that includes the signed Informed Consent form and copies of all source documentation related to that subject. The Investigator must ensure the reliability and availability of source documents from which the information on the CRF will be derived.

All study documents (patient files, signed informed consent forms, copies of CRFs, Study File Notebook, etc.) must be kept secured for a period of five years.

